**SECTION I: RESEARCH PLAN**

1. **Statement of Purpose:** State the scientific aim(s) of the study, or the hypotheses to be tested.

Aim 1: Does lactation improve insulin sensitivity and increase lipolysis in women?

In this Aim, we will assess whether lactation amongst women with a history of GDM will improve whole body insulin sensitivity as well as increase whole body lipid turnover by using hyperinsulinemic-euglycemic clamps combined with [6,6-2H]-glucose and [2H5]-glycerol infusions. These stable, non-radiating isotopes have been used extensively and safely to study the mechanisms of insulin resistance amongst non-pregnant as well as pregnant humans; however, these techniques have not previously been applied to the study of insulin sensitivity during lactation. Our goals will be two-fold: 1) to determine whether lactation induces similar changes in insulin sensitivity in humans as in mice and 2) to pilot the feasibility of performing larger, more detailed metabolic studies in this population of women post-partum.

Aim 2: Retrospective chart review of women with a history of GDM who had an OGTT 6-8 weeks post-partum as part of standard of care at Yale Medicine's Maternal-Fetal Medicine Clinic.

2. **Probable Duration of Project:** State the expected duration of the project, including all follow-up and data analysis activities.

5 years

3. **Background:** Describe the background information that led to the plan for this project. Provide references to support the expectation of obtaining useful scientific data.

Our premise is that lactation protects against the development of Type 2 Diabetes Mellitus (T2D) by mobilizing tissue triglycerides (TGs) and fully reversing the insulin resistance (IR) of pregnancy. A growing body of epidemiological data has indicated that nursing protects against T2D in all women but particularly amongst women with gestational diabetes mellitus (GDM) (1-8). However, no studies have investigated the detailed molecular mechanisms underlying these beneficial effects of lactation. Many studies have

demonstrated the importance of intracellular tissue TGs in the pathophysiology of IR and T2D (9). Our preliminary animal studies suggest that lactation lowers liver TG content in post-partum mice. Therefore, we hypothesize that lactation mobilizes tissue lipids post-pregnancy, which, in turn, improves insulin sensitivity. The goal of this study will be to investigate the mechanisms by which lactation prevents diabetes. Given the continued increase in T2D in the US and the world (10-12), understanding how breastfeeding improves the metabolic health of women will have potentially wide-ranging health benefits.

Nursing and Diabetes Risk. A growing number of epidemiological studies have reported a strong inverse relationship between lactation and the risk of developing T2D (1-8,13-16). The protective effects of lactation hold for all women but are particularly striking in those with a prior history of GDM (2,3,6,8,14). Several large cohort studies have shown that lactation reduced the risk of developing metabolic syndrome and/or T2D and that the degree of risk reduction increased with longer durations of breastfeeding (15,16). These initial cross-sectional studies relied on a self-report of diabetes and did not correct for potentially confounding differences in pre-pregnancy metabolic parameters, weight changes or life-style that might co-segregate with diabetes risk as well as the likelihood of successfully nursing ("reverse causation"). However, more recent prospective studies have addressed these concerns. The SWIFT study demonstrated that increasing lactation intensity and duration decreased the risk of subsequent biochemically defined diabetes by up to 57% over two years post-partum in women with previous GDM (4). Similarly, the 30-year follow up of the Cardia study demonstrated that lactation duration/intensity was associated a graded 25%-47% reduction in subsequent long-term risk of biochemically defined T2D in all women (5). Importantly, both of these studies controlled for confounding factors such as antecedent metabolic or life-style differences and both found that T2D risk reduction was independent of weight loss. Finally, Bajaj and colleagues followed a cohort of women over 3 years and showed that nursing for 12 months or more reduced the risk of prediabetes or T2D by 67% and correlated with persistent improvements in maternal insulin sensitivity (13). Therefore, lactation confers strong, independent, dose-dependent and long-lasting protection against T2D in parous women.

Maternal Metabolism during Pregnancy and Lactation. Pregnancy is associated with alterations in fuel metabolism that promote energy storage as fat. In early pregnancy, enhanced tissue insulin sensitivity coupled with elevated circulating insulin levels promotes lipogenesis and adipocyte fat storage (17-19). Pregnancy also stimulates hyperphagia and increased food intake contributes to maternal fat accumulation (20). As pregnancy advances, the initial insulin sensitivity transitions into increasing peripheral IR, which shunts nutrients and energy away from maternal tissues to the fetus. Increased maternal IR leads to increased fasting and post-prandial glucose levels, elevated TGs, increased hepatic gluconeogenesis, elevated rates of systemic lipolysis, and increased insulin secretion (21). During the latter part of pregnancy, decreased adipocyte lipoprotein lipase activity has been shown to reduce the uptake of TGs into maternal fat (20). Finally, as breast epithelial cells proliferate and differentiate during mid-pregnancy, they develop prominent cytoplasmic lipid droplets (22), resulting in significant storage of TGs in the mammary gland. The onset of lactation represents a shift to energy export via milk production. Milk fat, in particular, is an important source of energy for neonatal growth and lactating mice export up to 32 grams of TGs (approximately the weight of a female mouse) during 20 days of lactation (23). Three sources contribute to milk lipid: dietary fat, fatty acids mobilized from maternal stores, and de novo lipogenesis by mammary epithelial cells (23,24). As a result, lactating mothers respond to the metabolic demands of milk fat production through a combination of increased food consumption, the mobilization of stored TGs, and increased hepatic glucose production to supply substrates for de novo TG synthesis by mammary epithelial cells.

[figure not shown]
Insulin Resistance and Type 2 Diabetes Mellitus. In addition to pregnancy, IR is the earliest abnormality defined in patients at risk of T2D, typically preceding the onset of diabetes, sometimes for long periods of

time as part of a constellation of abnormalities known as “the metabolic syndrome” (25-29). Hyperglycemia only occurs when pancreatic beta-cells can no longer sustain the level of hyperinsulinemia required to offset the defects in insulin action that define IR (9). One of the major risk factors for T2D is overnutrition and obesity, (especially increased visceral adipose tissue), which is associated with elevated levels of circulating TGs and non-esterified free fatty acids (NEFAs) as well as the accumulation of TGs within hepatocytes and myocytes (9,26,27). Several studies have shown that intrahepatic and intramyocyte lipid accumulation is more predictive of IR than total body or visceral adiposity (9,29-35). Intracellular TG accumulation, in turn, is associated with increased cellular diacylglycerol (DAG) and ceramide levels, activation of novel protein kinase C (nPKC) isoforms and phosphorylation of the insulin receptor (at Thr1160), which inhibits its kinase activity (9,36-42). These findings provide a potential mechanistic framework for understanding how intracellular lipid accumulation may cause IR and lead to the development of T2D. It is unknown whether similar changes in intracellular TGs, DAGs and/or phosphorylation of the insulin receptor contribute to changes in insulin sensitivity during reproductive cycles.

While accumulating evidence demonstrates that breastfeeding reduces the risk of developing T2D, the mechanisms mediating this risk reduction are unknown. We propose that the reduction in risk of T2D is a consequence of changes in fuel and energy metabolism associated with the metabolic demands of milk production. Decreases in plasma glucose and insulin levels during lactation likely contribute to lipid mobilization from maternal stores, allowing NEFAs to be redirected from peripheral tissues to the lactating mammary gland in order to support milk TG secretion (43,44). Thus, our working hypothesis is that lactation mobilizes lipids from maternal tissues to be used for milk secretion and, in turn, this improves insulin sensitivity in women who lactate. We hypothesize that those who do not lactate have persistent pregnancy-related intracellular lipid storage and IR, increasing their long-term risk of T2D.

4. **Research Plan:** Summarize the study design and research procedures using non-technical language that can be readily understood by someone outside the discipline. **Be sure to distinguish between standard of care vs. research procedures when applicable, and include any flowcharts of visits specifying their individual times and lengths.** Describe the setting in which the research will take place.

**Aim 1:** Two groups of 16 women with a history of GDM will be recruited for participation. Group 1 will consist of women who exclusively or mostly breast-fed for at least 4-6 months (< 6 ounces of formula/24 hours at 6-9 weeks of delivery) and who delivered within the past 18 months; Group 2 will consist of women who exclusively or mostly formula-fed (no breastfeeding or < 3 weeks of breastfeeding) and who delivered within the past 18 months.

**Post-partum OGTT visit (standard of care):** 6-8 weeks after delivery, patients from the Yale Medicine’s Maternal-Fetal Medicine Clinic with a history of GDM during pregnancy undergo an OGTT as part of standard of care. At this visit, they may be approached by research staff about participating in this study. If they are interested in participating, they will sign the consent form at this visit and they will then be

asked to complete questionnaires assessing their infant feeding practices, including, but not limited to, overall experience (sources of support, barriers/difficulties faced), frequency/number of feeds, and type of feeds (breastfeeding, expressed breastmilk, formula). Women who are lactating will be given the option to provide us with 2-4 mL of expressed breastmilk, which will be kept frozen and its metabolite content will be studied, including milk lipids, protein, lactose and nucleic acids. The breastmilk will be stored for the duration of the study and will not be shared.

Approximately 8 weeks later, these women will be contacted by research staff and asked about their infant feeding practices. If their feeding practices match the description of Group 1 or Group 2, they will be invited to return for Visit 1, Visit 2 and Visit 3 (described below).

Screening visit (Visit 1): For women who did not attend the post-partum OGTT visit or who are not patients at the MFM Clinic, they will be consented at this visit. All participants will be screened at the YNHH Research Unit (HRU) or Church Street Research Unit (CSRU) with a medical history and exam. Blood will be collected for HbA1C, Cr, ALT, AST, TSH, hematocrit and fasting lipid panel, and a urine pregnancy test will be administered. Oral glucose tolerance tests (OGTT) will be performed after an overnight fast. A nurse will insert an intravenous (IV) catheter and subjects will ingest 7.5 oz of glucola, which contains 75 g of glucose in flavored water. Blood samples will be taken at certain time points before and after glucola ingestion for the measurement of plasma glucose and insulin concentrations. Approximately 60 mL of blood will be drawn at this visit.

Continuous glucose monitor (CGM) placement (Visit 2): For up to 10 days prior to Visit 3, eligible participants will be asked to wear a CGM (Dexcom G6 Pro). At the visit for CGM placement (either at CSRU or HRU): 1) a trained study staff member will explain to the participant how to use the CGM, and 2) a trained study staff member will insert the CGM's plastic wire-like tip under the participant's skin with the use of the CGM applicator. This visit will take approximately 15 minutes.

The CGM consists of a sensor that measures glucose levels from the interstitial tissue. A transmitter that captures and stores data from sensor. The sensor is sterile and comes in an unopened package. Each sensor and transmitter are single use only and disposable. The Dexcom G6 Pro does not require any calibration. This means that no finger sticks are required for its use. Participants will need to return the sensor within 30 days of sensor placement.

The Dexcom G6 Pro data is blinded to study participants. Study staff will explain to the participants that intense exercise may cause the sensor to loosen due to sweat or movement of the sensor. If the CGM sensor/transmitter falls off while the participant is wearing it, we will ask them to return to the HRU or CSRU so that a new sensor/transmitter can be re-inserted. Subjects will be provided with our contact information in the event that they have any questions, concerns or issues related to the CGM.

After completing the 10-day CGM session, the sensor will be removed by a trained study staff member. To remove the sensor, the adhesive patch will be gently peeled off from the skin. Removal of the sensor is a painless procedure. The sensor/transmitter will be discarded after use. CGM removal will occur during Visit 3.

Hyperinsulinemic-euglycemic clamp (Visit 3): After an overnight fast, eligible subjects will return to the YNHH HRU. Two IV catheters will be inserted: one into a distal arm or hand vein that will be placed in a heated box to allow for the sampling of arterialized venous blood; the second into an antecubital vein for administration of a primed (200 mg/m^2) and continuous infusion of [6,6-2H] Glucose and [2H5] Glycerol

(non-radioactive stable isotopes) as well as for collecting blood samples for insulin and glucose measurements. After an equilibration period lasting 2 hours., the 2-step euglycemic-hyperinsulinemic clamp study will be performed. A primed-continuous infusion of regular insulin will be given at 8 mU/(m^2 × min) during the first 2 hours, and increased to 40 mU/(m^2 × min) for the subsequent 2 hours. Plasma glucose levels will be measured every 5 min, and a variable glucose infusion will be initiated to maintain levels at ~90 mg/dl. Plasma samples will be drawn at baseline and throughout the infusion period for measurement of isotope enrichment, insulin, NEFA, glycerol turnover, and additional hormones which may be altered with lactation. Approximately 160 mL of blood will be drawn at this visit.

Also at this visit, we will perform indirect calorimetry a total of 3 times (once before and twice during the insulin clamp). A transparent plastic hood will be placed over the participant's head for 30 minutes each time. A hose connects the hood to a calorimeter, which measures oxygen consumption and carbon dioxide production and calculates resting energy expenditure.

After the insulin clamp is completed, body composition will be assessed using whole body DXA. The DXA scan will be performed in the HRU to measure fat distribution, body fat, lean body mass and bone density.

Questionnaires: Women will be asked to complete questionnaires assessing their infant feeding practices, including, but not limited to, overall experience (sources of support, barriers/difficulties faced), frequency/number of feeds prior to introduction of solid foods, and type of feeds (breastfeeding, expressed breastmilk, formula). These questionnaires can be completed on a computer or smart phone at the woman's convenience. The questionnaires will be adapted from the CDC (<https://www.cdc.gov/breastfeeding/data/ifps/questionnaires.htm>) and the "Breastfeeding Self-Efficacy Scale".

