#### Aim 2: Retrospective chart review

1. Estimated number of records to be reviewed: 500/year
2. Criteria for inclusion/exclusion: Women with a history of GDM who had an OGTT 6-8 weeks post-partum as part of standard of care at Yale Medicine's Maternal-Fetal Medicine Clinic in the past 3 years and throughout the duration of this study. (May 1,2016 until April 30, 2024)
3. Information collected and recorded from medical records:
  - a. Data to be recorded from the chart:
    - i. MRN
    - ii. Sociodemographic information (age, race/ethnicity, preferred language, marital status, insurance, tobacco use)
    - iii. Pre-pregnancy height/weight/BMI
    - iv. GDM history (date of diagnosis, management)
    - v. Date of delivery and delivery method
    - vi. Weight/BMI on day of delivery
    - vii. Gravida and parity
    - viii. Date of OGTT during pregnancy and post-partum
    - ix. OGTT lab results (during pregnancy and post-partum)
    - x. Weight/BMI on day of OGTT (during pregnancy and post-partum)
    - xi. Infant feeding practices
    - xii. Infant birth weight/percentile and weight/percentile at 2 months of age

- b. Type of medium that will be used to record the information and the plans for maintaining confidentiality and security of the data: CSV file. The file will be stored on a secured server on an encrypted laptop and/or computer that is stored in a locked office.
- c. Who will have access to the data, and how access to the data storage (whether paper-based or electronic) will be monitored: All data will be available to study personnel and stored on a secured server on an encrypted laptop and/or computer that is stored in a locked office.

4. How will the data and/or identifiers be destroyed when no longer needed for research purposes? If it will not please explain why data must be retained, for how long and how it will be kept secured: All data comes from the EPIC EMR and therefore cannot be destroyed and will be retained indefinitely. All de-identified data will be stored on a secured server on an encrypted laptop and/or computer that is stored in a locked office.

5. Genetic Testing      N/A

6. **Subject Population:** Provide a detailed description of the types of human subjects who will be recruited into this study.

Aim 1:

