### 13. Statistical Considerations: Describe the statistical analyses that support the study design.

Group sample sizes of 15 and 15 achieve 80% power to detect a between-group difference of 0.61 in a design with 7 repeated measurements (taken at time 0, 5, 10, 30, 60, 90, 120 min) having a autoregressive AR(1)

covariance structure when the standard deviation is 1, the correlation between observations on the same subject is 0.6, and the alpha level is 0.05. To account for up to 5-10% missing data due to drop out or poor quality data, we will need to enroll a total of 32 subjects (16 per group) for this study. Data Analysis: Primary endpoints: Whole body insulin sensitivity, endogenous glucose production, whole body lipid turnover rates. Secondary endpoints: Plasma NEFA, TGs, insulin levels, metrics of body composition. Statistical Analysis: Before statistical testing, all continuous variables will be tested for normality of distribution. Summary statistics will be computed. For between-group comparisons of patient characteristics, two sample t-test or Mann-Whitney U test will be used for continuous variables, and Fisher's exact test for categorical variables. Comparisons of repeatedly measured glucose and lipid turnover rates will be made using the mixed model analysis. Fixed factors include group and time and their interactions. A random effect for subject plus an autoregressive covariance matrix will be used to accommodate within-subject correlation of repeated assessments. Linear contrasts comparing differences between groups or different time points within a group will be estimated.

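### Aim 1 asks a causal question of self-selected feeding groups with no adjustment, and the reason for early stopping, which the planned questionnaire could supply, is not used in the analysis

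*Combined protocol and SAP*

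**What the plan says.** All references are to Section I of the combined protocol and SAP.

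- **Aim (item 1).** The question is put causally: does lactation improve insulin sensitivity and increase lipolysis?
- **Groups (item 4, Aim 1; repeated in item 6).** "Group 1 will consist of women who exclusively or mostly breast-fed for at least 4-6 months", whereas "Group 2 will consist of women who exclusively or mostly formula-fed (no breastfeeding or < 3 weeks of breastfeeding"). No condition is set on why a woman did not start or why she stopped.
- **Background (item 3, Nursing and Diabetes Risk).** Earlier cross-sectional studies are faulted for not correcting for differences in pre-pregnancy "metabolic parameters, weight changes or life-style that might co-segregate with diabetes risk as well as the likelihood of successfully nursing". The protocol calls this reverse causation. It credits two later prospective studies because "both of these studies controlled for confounding factors such as antecedent metabolic or life-style differences".
- **Analysis (item 13).** "Fixed factors include group and time and their interactions". No covariate, matching or sensitivity analysis is stated.
- **Questionnaire (item 4).** It covers "overall experience (sources of support, barriers/difficulties faced"). No use of the answers in grouping or analysis is described. The Questionnaires paragraph lets women complete it when convenient, so it need not precede the clamp.
- **Chart review (Aim 2).** "Pre-pregnancy height/weight/BMI", GDM management and OGTT results during pregnancy are extracted at the Maternal-Fetal Medicine Clinic. Aim 1 does not name them as covariates.

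**The concern.** The women chose, or arrived at, their feeding group. Group 1 is selected on success. Group 2 contains women who never tried and women who tried and stopped early. If poorer metabolic health before or during pregnancy makes sustained nursing less likely, such women are under-represented in Group 1 and over-represented in Group 2. The plan would then credit lactation with a difference that was there beforehand. The bias would point the way the hypothesis points, so a positive result is the one it would make hardest to interpret.

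No Aim 1 measurement settles the matter. The clamp is done once, and women who are lactating or have lactated within a month of screening are excluded, so it follows weaning. The 6-8 week OGTT comes after a woman who nursed for less than 3 weeks has already stopped.

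**Working it through.** **1. The plan's own figure.** Inputs from item 13: 15 per group, difference 0.61, SD 1, seven measurements, AR(1) with correlation 0.6, alpha 0.05. Taking 0.6 as the correlation between successive measurements, the variance of the seven-value mean is

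[7 + 2(6×0.6 + 5×0.36 + 4×0.216 + 3×0.1296 + 2×0.07776 + 0.046656)]/49 = 20.710/49 = 0.423.

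The standard error of the group difference is √(0.423×2/15) = 0.237, and 0.61/0.237 = 2.57. On 28 df, power is 0.81 one-sided and 0.70 two-sided. The stated 80% reproduces one-sided; the plan does not state sidedness. I use two-sided 5% below.

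**2. How large could the bias be?** The documents give neither the share of Group 2 affected nor the size of the shift, so both are assumed. Let a share f of Group 2 have values d SD less favourable at every time point, with no true lactation effect.

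- Spurious mean difference: f×d.
- Group 2 variance: V + f(1−f)d², because Group 2 is then a mixture. V = 1 for one value per woman, V = 0.423 for the seven-value mean.
- Standard error: √{[2V + f(1−f)d²]/15}.
- Rejection rate: noncentral t on 28 df, with noncentrality f×d divided by the standard error.

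Worked case, f = 0.5 and d = 1, seven-value mean: the difference is 0.50; the standard error is √[(0.845 + 0.25)/15] = 0.270; the noncentrality is 1.85; the rejection rate is 43%.

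| f | d | Spurious difference (SD) | Rejection, one value | Rejection, seven-value mean |
|---|---|---|---|---|
| 0.3 | 0.5 | 0.15 | 7% | 9% |
| 0.3 | 1.0 | 0.30 | 12% | 19% |
| 0.5 | 0.5 | 0.25 | 10% | 17% |
| 0.5 | 1.0 | 0.50 | 24% | 43% |

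Simulating the first and last rows gave the same figures to within half a percentage point. Leaving out the mixture variance would give 26% and 53% in the last row, which overstates the upper end.

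**3. What would reproduce the whole design difference?** It needs d = 0.61/f: 0.61/0.3 = 2.03 SD, or 0.61/0.5 = 1.22 SD. A bias as large as 0.61 therefore needs a large share, a large shift, or both.

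**4. What the sensitivity analysis costs.** Leaving out 30-50% of 15 Group 2 women leaves about 11 to 8. The standard error becomes √[0.423(1/15 + 1/n)], which is 0.258 for n = 11 and 0.285 for n = 8. Two-sided power for 0.61 falls from 0.70 to 0.62 and 0.53.

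**The case against.** The strongest reply is that early stoppers are the wrong target. Group 1 is selected on 4-6 months of success, and never-starters may differ metabolically or in life-style too. A Group 2 made up only of never-starters would remain open to the confounding that the Background describes. This stands: the central gap is the unadjusted comparison in item 13, and the definition of Group 2 is one route into it.

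A reader might go further and infer that women whose nursing failed for metabolic reasons are known to be in Group 2, or that the protocol itself says insulin resistance prevents nursing. The documents support neither. The definition admits such women but gives no numbers or reasons. The Background speaks of differences "that might co-segregate with diabetes risk as well as the likelihood of successfully nursing"; it does not mention milk supply. That mechanism is an assumption here.

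A reader might also infer that covariate adjustment is useless because insulin sensitivity before lactation is not measured. That is true only of complete removal. Adjustment for an antecedent measure can reduce the bias across the whole comparison, never-starters included.

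Three further points carry some weight. Excluding prior diabetes and HbA1C of 6.5% or more narrows metabolic differences, but does not equalise insulin sensitivity. Feasibility is one of the two goals of Aim 1, but the other is to determine the effect on insulin sensitivity, and item 13 gives a power statement and primary endpoints. Clinic-recruited women are already asked about barriers at 6-8 weeks, so part of the information will exist; what is missing is its collection from everyone before the clamp, and a stated use.

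**Conclusion.** The point holds as a cheap improvement. As written, the plan could attribute to lactation a metabolic difference that preceded it, and it does not use information it already means to collect. On the assumed values, the chance of a false positive ranges from slightly above nominal (7-9%) to well above it (24-43%). The size rests entirely on f and d, which the documents do not give. It also rests on a constant shift over time, 15 analysable women per group, two-sided testing and AR(1) correlation by measurement order.

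The documents do not show that the bias is present, that pooling early stoppers is its main cause, or that removing them would cure it. If the difference persists without the women who stopped for insufficient milk, that is necessary but not sufficient for a causal reading. If it loses statistical significance, that says little, given the loss of power.

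**What to change.** 1. **Collection.** From the barriers and difficulties part of the planned questionnaire, obtain from every participant, before the clamp, the reason for not starting or for stopping.
2. **Sensitivity analysis.** In item 13, pre-specify a repeat of the primary contrasts that leaves out Group 2 women who stopped for insufficient milk. Report it as an estimate with a confidence interval beside the main result, not as a significance rule.
3. **Adjustment.** Alongside it, pre-specify adjustment for one or two antecedent metabolic measures that the Aim 2 chart review already extracts, such as pre-pregnancy BMI or the pregnancy OGTT result, where available for Aim 1 women. Women recruited from outside the clinic may lack these data, so state how gaps will be handled.
4. **Wording.** State the conclusion as an association.

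I would not steer recruitment towards never-starters: they may differ in life-style, so one confounder could replace another.

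The cost is one mandatory questionnaire item with a fixed time, some chart extraction and two further model runs, with no new visit or procedure. The sensitivity estimate is less precise, as shown in the working, and about 15 women per group support no more than one or two covariates.
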